## **5.2. Breaking the Blind**

At the initiation of the study, the study site will be instructed on the method for breaking the blind. The method will be either a manual or an electronic process. Blinding codes should only be broken in emergency situations for reasons of subject safety. In this observer-blinded study, the study staff dispensing and administering the vaccine will be unblinded, but all other study personnel, including the principal investigator and the sponsor, will be blinded. In particular, the individuals who evaluate subject safety as well as the subject will be blinded. Because the study vaccines are different in physical appearance, the study vaccine syringes will be labeled in a manner that prevents the study subjects from identifying the vaccine type based on its appearance.

The responsibility of unblinded dispenser and administrator must be assigned to an individual or individuals who will not participate in the evaluation of any study subjects. Contact between the unblinded dispenser and study subjects and unblinded administrator and study subjects should be kept to a minimum. The remaining site personnel must not know investigational product assignments.

In case of an emergency, when knowledge of the investigational product assignment is required for the medical management of an individual subject, it may be unblinded. The investigator must notify a member of the study team immediately after determining that it is necessary to unblind the assignment. The investigator must also indicate in source documents that the blind was broken and provide the date and reason for breaking the blind. Any AE or SAE associated with breaking the blind must be recorded and reported as specified in this protocol.

## **5.3. Subject Compliance**

All doses of investigational product will be administered by the appropriately designated study staff at the investigational site.

## **5.4. Investigational Product Supplies**

### **5.4.1. Dosage Form(s) and Packaging**

Bivalent rLP2086 (containing 60 µg each of a purified subfamily A and subfamily B rLP2086 protein, adsorbed to aluminum in a sterile buffered isotonic suspension) is provided in a 0.5-mL dose for injection.

The bivalent rLP2086 final formulation is described in Table 2.

**Table 2. Bivalent rLP2086 Investigational Product Formulation**

The investigational products (bivalent rLP2086, HAV vaccine, and saline) will be provided by the sponsor to each study site. Study vaccines will be packed and labeled as investigational product in accordance with current guidelines and applicable local and legal regulatory requirements. Each investigational product will be labeled with a unique dispensable unit (DU) or container number.

A licensed pediatric HAV vaccine will be provided in a 0.5-mL dose for injection. Information on which licensed pediatric HAV vaccine is to be used is contained in the investigational product manual.

The placebo consists of sterile saline solution for injection (0.85% sodium chloride) supplied as a 0.5-mL dose.

### 5.4.2. Preparation and Dispensing

See the dosage and administration instructions (DAI) or package insert for instructions on how to prepare the investigational product for administration. Investigational product should be prepared and dispensed by unblinded appropriately qualified and experienced member of the study staff (eg, physician, nurse, physician's assistant, practitioner, or pharmacist) as allowed by local, state, and institutional guidance. The investigational product will be administered to subjects who are blinded.

## 5.5. Administration

Standard vaccination practices must be observed and vaccine must not be injected into blood vessels. Appropriate medication and other supportive measures for management of an acute hypersensitivity reaction should be available in accordance with local guidelines for standard immunization practices.

Administration of investigational products should be performed by an appropriately qualified, Good Clinical Practice (GCP)-trained, and vaccine-experienced member of the study staff (eg, physician, nurse, physician's assistant, practitioner, pharmacist, or medical assistant) as allowed by local, state, and institutional guidance. In this observer-blinded study, the study staff dispensing and administering the vaccine will be unblinded, but all other study personnel, including the principal investigator and the sponsor, will be blinded.

Investigational product administration details (ie, date of administration, container number, volume, route, and site of administration, administration errors) will be recorded on the CRF.

During the study, subjects in Group 1 will be administered bivalent rLP2086 by intramuscular injection at Months 0, 2, and 6 into the upper deltoid muscle of the arm.

Subjects in Group 2 will be administered HAV vaccine/saline/HAV vaccine at Months 0, 2, and 6 into the upper deltoid muscle of the arm.

### **5.6. Investigational Product Storage**

The investigator, or an approved representative, eg, pharmacist, will ensure that all investigational products, including any comparative agents and/or marketed products, are stored in a secured area with controlled access under recommended storage conditions and in accordance with applicable regulatory requirements.

Investigational product should be stored in its original container and in accordance with the vaccine label. For storage, the preferred orientation of the vaccine is horizontal. See the DAI or package insert for storage conditions of the product.

Storage conditions stated in the SRSD will be superseded by the storage conditions stated in the labeling.

All vaccines will be shipped at +2°C to +8°C to each study site upon request. Upon receipt at the study site, the vaccines should be immediately transferred to a +2°C to +8°C temperature-monitored refrigerator for storage.

Site systems must be capable of measuring and documenting (for example, via a log), at a minimum, daily minimum and maximum temperatures for all site storage locations (as applicable, including frozen, refrigerated, and/or room-temperature products). This should be captured from the time of investigational product receipt throughout the study. Even for continuous monitoring systems, a log or site procedure that ensures active daily evaluation for excursions should be available. The operation of the temperature monitoring device and storage unit (for example, refrigerator), as applicable, should be regularly inspected to ensure it is maintained in working order.

Any excursions from the product label storage conditions should be reported upon discovery. The site should actively pursue options for returning the product to labeled storage conditions, as soon as possible. Deviations from the storage requirements, including any actions taken, must be documented and reported to the sponsor.

Once an excursion is identified, the investigational product must be quarantined and not used until the sponsor provides documentation of permission to use the investigational product.

Specific details regarding temperature monitoring, procedures for the review of temperature deviations, and information the site should report for each excursion will be provided to the site in the investigational product manual.

Receipt of materials, door opening and closing, and other routine handling operations where the product(s) are briefly out of labeled temperature range are not considered excursions.

### **5.7. Vaccine Accountability**

The investigator's site must maintain adequate records documenting the receipt, use, loss, or other disposition of the vaccine supplies.

Unused investigational product may be destroyed according to procedures and local environmental regulations after all investigational product accountability documentation has been completed, unless there are regulatory requirements for this to be returned. Empty investigational product containers may be destroyed after the sponsor has performed accountability. Only outer containers are used to perform accountability while syringes are discarded at the point of use. Investigational product return must be documented on the accountability log.

The sponsor or designee will provide guidance on the destruction of unused investigational product (eg, at the site).

### **5.8. Concomitant Treatment**

The name and date of administration of any nonstudy vaccine (or allergen immunotherapy) given from the signing of the ICD up to Visit 6 will be recorded on the CRF.

The name, start and stop date, and route of administration for concomitant medications (prescription and nonprescription) used to treat an AE (excluding events recorded only in electronic diary [e-diary]) from the signing of the ICD to Visit 7 will be recorded in the CRF.

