## PROTOCOL SUMMARY

### Background and Rationale

*Neisseria meningitidis* is a leading cause of bacterial meningitis in infants, adolescents, and young adults. In particular, *N meningitidis* serogroup B (MnB) is responsible for approximately two-thirds of the cases of observed meningococcal infections in Europe, with an overall case-fatality rate of 6% to 8% from 1999 to 2006. MnB disease accounts for approximately one-quarter of meningococcal cases seen in North America in the areas participating in the Active Bacterial Core surveillance program. There is substantial morbidity among survivors, including neurological disability, limb loss, and hearing loss.

A recombinant, multicomponent MnB vaccine (Bexsero) is licensed in Europe, Canada, Australia, Chile, and the United States. Trumenba® (bivalent recombinant lipoprotein 2086 vaccine [bivalent rLP2086]), developed by Pfizer, is approved in the United States for use in individuals 10 through 25 years of age for active immunization to prevent invasive meningococcal disease (IMD) caused by MnB. Recommendations for MnB vaccination are under consideration in various countries. However, to date, no broadly effective vaccine against MnB disease is available worldwide. General availability of a safe and immunogenic MnB vaccine remains an unmet medical need, and a successful vaccine will provide substantial improvement in prevention of meningococcal infection and a reduction in the burden of disease.

Bivalent rLP2086 is targeted to a conserved, surface-exposed lipoprotein, lipoprotein 2086 (LP2086), a meningococcal virulence factor that binds human factor H. *N meningitidis* serogroup B recombinant lipoprotein 2086 (rLP2086) has been expressed in *Escherichia coli* and formulated in a bivalent vaccine composed of 1 subfamily A strain and 1 subfamily B strain of rLP2086.

This study will assess the immunogenicity, safety, and tolerability of bivalent rLP2086 (final formulation) administered as a Month 0, 2, and 6 schedule in healthy subjects aged  $\geq 24$  months to  $< 10$  years. Randomization will be stratified to ensure that equal numbers of subjects are included in the  $\geq 24$ -month to  $< 4$ -year age group and the  $\geq 4$ -year to  $< 10$ -year age groups.

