## SCHEDULE OF ACTIVITIES

The schedule of activities table provides an overview of the protocol visits and procedures. Refer to the [Study Procedures](#) and [Assessments](#) sections of the protocol for detailed information on each procedure and assessment required for compliance with the protocol.

The investigator may schedule visits (unplanned visits) in addition to those listed on the schedule of activities, in order to conduct evaluations or assessments required to protect the well-being of the subject.

Visit Identifier	Visit 1	Visit 2	Visit 3	Visit 4	Visit 5	Visit 6	Visit 7
Approximate month	0	1	2	3	6	7	12
Visit description	Vaccination 1	Post–Vaccination 1 Follow-up	Vaccination 2	Post–Vaccination 2 Blood Draw	Vaccination 3	Post–Vaccination 3 Blood Draw	Month 12 Follow-up and Blood Draw
Visit window	Day 1	25 to 35 Days After Visit 1	42 to 70 Days After Visit 1	28 to 42 Days After Visit 3	105 to 126 Days After Visit 3	28 to 42 Days After Visit 5	168 to 196 Days After Visit 5
Informed consent	X						
Review eligibility criteria	X						
Confirm continued eligibility		X	X	X	X	X	X
Demography	X						
Medical history and physical examination	X						
Record previous PRP-OMP vaccinations	X						
Record previous vaccines with any meningococcal, DTaP, or HPV vaccine antigens	X						
Temperature (measured as appropriate for age)	X		X		X		

Visit Identifier	Visit 1	Visit 2	Visit 3	Visit 4	Visit 5	Visit 6	Visit 7
Approximate month	0	1	2	3	6	7	12
Visit description	Vaccination 1	Post–Vaccination 1 Follow-up	Vaccination 2	Post–Vaccination 2 Blood Draw	Vaccination 3	Post–Vaccination 3 Blood Draw	Month 12 Follow-up and Blood Draw
Visit window	Day 1	25 to 35 Days After Visit 1	42 to 70 Days After Visit 1	28 to 42 Days After Visit 3	105 to 126 Days After Visit 3	28 to 42 Days After Visit 5	168 to 196 Days After Visit 5
Urine pregnancy test (only for female subjects biologically capable of having children)	X		X		X		
Collect blood sample a	X			X		X	X
Randomization	X						
Vaccination and observation	X		X		X		
Record nonstudy vaccinations		X	X	X	X	X	
Provide e-diary, thermometer, measuring tape/ruler, and caliper if required	X		X		X		
Review e-diary		X		X		X	
Collect e-diary				X		X	
Assess reactogenicity b	Days 1-7		Days 1-7		Days 1-7		
Record the use and type of antipyretic medication	Days 1-7		Days 1-7		Days 1-7		
(S)AE collection appropriate to the visit	X	X	X	X	X	X	X
Provide the parent(s)/legal guardian with a memory aid						X	

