#### **2.1.3. Secondary Objectives**

- To describe the immune response as measured by hSBA performed with 4 primary MnB test strains, 2 expressing an LP2086 subfamily A protein and 2 expressing an LP2086 subfamily B protein, measured 1 month after the third vaccination with bivalent rLP2086, in healthy subjects aged  $\geq 24$  months to  $< 10$  years at study entry (ie, in both age strata combined).

- To describe the immune response as measured by hSBA performed with 4 primary MnB test strains, 2 expressing an LP2086 subfamily A protein and 2 expressing an LP2086 subfamily B protein, measured 1 month after the second vaccination and 6 months after the third vaccination with bivalent rLP2086, in healthy subjects aged  $\geq 24$  months to  $< 4$  years at study entry, in healthy subjects aged  $\geq 4$  years to  $< 10$  years at study entry, and in both age strata combined.

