### **5.9. Prohibited During the Study**

- Prophylactic antipyretics and other pain medications to prevent symptoms associated with investigational product are not permitted. If the subject has received such medications prior to a planned administration of investigational product, vaccination should be temporarily delayed as specified in [Section 4.3](#).
- Receipt of any blood products, including immunoglobulin.
- Nonstudy meningococcal vaccines or vaccines containing all or individual antigens included in DTaP or HPV vaccines are not permitted before Visit 3 and within 28 days of any study vaccination.

- Receipt of any other serogroup B meningococcal vaccine is prohibited throughout the course of the study.
- Other nonlive or live nonstudy vaccines are not permitted within 14 and 28 days, respectively, of any study vaccination.
- Intramuscular/sublingual allergen immunotherapy is not permitted within 14 days of any study vaccination.
- Systemic (oral, intravenous, or intramuscular) corticosteroid therapy within 28 days of any study vaccination.

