#### **5.10. Permitted During the Study**

- Nonstudy vaccines used in the event of a disease outbreak or pandemic are allowed. However, while prioritizing standard clinical care, efforts should be made not to administer nonstudy vaccines within 14 days (for nonlive vaccines) or 28 days (for live vaccine) as specified below.
- Nonstudy vaccines (other than any meningococcal vaccines and vaccines containing all or individual antigens included in DTaP and HPV vaccines) that are part of recommended immunization schedules are allowed anytime during the study but should not be administered within 14 days (for nonlive vaccines) and 28 days (for live vaccines) of study vaccine administration. Please refer to [Section 5.9](#) regarding restrictions on administration other serogroup B meningococcal vaccines and vaccines containing all or individual antigens included in the DTaP and HPV vaccines.
- Antipyretics and other pain medications to treat symptoms associated with investigational product are permitted.
- A local anesthetic may be used at the site of the blood draw.
- Topical antibiotics are permitted.
- Topical and inhaled corticosteroids are permitted.

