6.3.2. Nonstudy Vaccination

Any *Haemophilus influenzae* type b conjugate vaccine (polyribosylribitol phosphate outer membrane protein: PRP-OMP) received prior to the signing of the ICD will be recorded in the case report form (CRF).

Any nonstudy vaccine given from the signing of the ICD to the blood draw at Visit 6 will be recorded in the CRF.

Nonstudy vaccines will be categorized according to the WHO Drug Dictionary (WHODRA).

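### Nonstudy vaccines are not recorded after Visit 6, so another MnB vaccine given before the Month 12 blood draw can enter the secondary hSBA results without a prompted CRF record

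*Protocol*

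**What the plan says.** **Endpoint.** Protocol 2.1.3 includes the response "measured 1 month after the second vaccination and 6 months after the third vaccination with bivalent rLP2086". Section 2.2.3 turns this into proportions at or above LLOQ, titer-threshold proportions and GMTs at that time point. SAP 8.2.2 analyses them in both the evaluable and the mITT populations.

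**Prohibition.** Protocol 5.9: "Receipt of any other serogroup B meningococcal vaccine is prohibited throughout the course of the study".

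**Recording.** Protocol 5.8 limits collection: the name and date of "any nonstudy vaccine (or allergen immunotherapy) given from the signing of the ICD up to Visit 6 will be recorded on the CRF". SAP 6.3.2 agrees: "Any nonstudy vaccine given from the signing of the ICD to the blood draw at Visit 6 will be recorded in the CRF". In the Schedule of Activities the row "Record nonstudy vaccinations" is marked at Visits 2 to 6 and blank at Visit 7. Sections 6.3 to 6.7 each carry the matching instruction; 6.8 (Visit 7) does not. SAP 8.2.6.4 summarises nonstudy vaccines only before vaccination and during the vaccination phase.

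**Context.** The Background states: "A recombinant, multicomponent MnB vaccine (Bexsero) is licensed in Europe, Canada, Australia, Chile, and the United States". It adds that countries are still considering recommendations on MnB vaccination. Section 5.10 says: "Nonstudy vaccines used in the event of a disease outbreak or pandemic are allowed".

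**The concern.** The study-long prohibition protects the Month 12 titers, but the data needed to verify it are collected only to about Month 7. If a child receives another MnB vaccine after Visit 6, and that vaccine induces bactericidal antibody against a test strain, the Visit 7 titer reflects two products. In Group 1 it would be read as persistence of the response to bivalent rLP2086; in Group 2, as background immunity. On that assumption the error goes one way, upward.

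The SAP gives receipt of a prohibited vaccine as an example of an important protocol deviation, which removes a child from the evaluable population. For Visit 7 data, that rule depends on information that no CRF field asks for.

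**Working it through.** **1. Length of the unrecorded period.** Visit 6 falls 28 to 42 days after Visit 5, and Visit 7 falls 168 to 196 days after Visit 5 (Schedule of Activities).

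- Shortest gap: 168 − 42 = 126 days, which is 126/168 = 75% of the time from dose 3 to the Month 12 sample.
- Longest gap: 196 − 28 = 168 days, which is 168/196 = 86%.

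**2. Other routes by which the vaccine could be recorded.**

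- Concomitant medication runs to Visit 7, but only for drugs that treat an AE (5.8).
- Preventive-care visits not associated with an AE are not collected (7.8.4).
- The AE checklist and the memory aid cover illnesses, diagnoses and medical-facility visits, not vaccines (6.7, 6.8, 7.8.5).
- The Schedule has a continued-eligibility tick at Visit 7, and 6.8 asks for a check against the withdrawal criteria. Neither names vaccines or provides a field for product and date.

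**3. What each analysis set does with such a child.**

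- mITT (SAP 5.1) needs only a valid, determinate result, so the child is always counted.
- Evaluable (SAP 5.2): the criteria are written for the primary endpoint, and the eligibility criterion ends one month after dose 3. The no-important-deviation criterion has no time limit, so the child is excluded only if the vaccination comes to light and the medical monitor classes it as important. No separate evaluable set is defined for Month 12.

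**4. Number of children per cell.** SAP Table 2 reproduces: 200×2 + 200×2 = 800 results per visit, and 4 × 800 = 3,200 in total. Protocol 7.1.2 keeps the 3:1 ratio and the equal age strata within each half.

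- Group 1: 300 / 2 strata × 50% = 75 per strain and stratum.
- Group 2: 100 / 2 strata × 50% = 25 per strain and stratum. Each child is tested on both strains of the assigned pair, so there is no further split.

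**5. Effect of one child**, if that child reaches LLOQ only because of the other vaccine:

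- Group 1: 1/75 = 1.3 points.
- Group 2: 1/25 = 4 points.

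If the child's titer rose 16-fold (an assumption), the GMT would be multiplied by 16^(1/75) = 1.04 in Group 1 or 16^(1/25) = 1.12 in Group 2.

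**6. Effect of a vaccinated fraction.** Let q be the fraction vaccinated outside the study and p the true Month 12 proportion. If every vaccinated child is at or above LLOQ at Visit 7, the observed proportion rises by q(1 − p). This is an upper bound. In percentage points:

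| q | p = 20% | p = 40% | p = 60% | p = 80% |
|---|---|---|---|---|
| 1% | 0.8 | 0.6 | 0.4 | 0.2 |
| 2% | 1.6 | 1.2 | 0.8 | 0.4 |
| 5% | 4.0 | 3.0 | 2.0 | 1.0 |
| 10% | 8.0 | 6.0 | 4.0 | 2.0 |

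For comparison, the Clopper-Pearson 95% interval at 40% is 28.9% to 52.0% with 30/75 (one stratum, Group 1) and 32.1% to 48.3% with 60/150 (strata combined). The documents give neither q nor p; both are illustrative.

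**The case against.** **The plan is not blind to the event.** Section 6.8 requires a check of the withdrawal criteria. Section 6.10 says the exclusion criteria should be considered, lists protocol violation as a reason for withdrawal, and puts the circumstances on the study outcome CRF. Exclusion criterion 1 is prior vaccination with a serogroup B vaccine. SAP 5.5.2 compiles all deviations before database closure, and SAP 8.2.6.1 lists violators. A reader might infer that a child vaccinated elsewhere is bound to be counted and that the sponsor could never find out. The documents do not support that for the evaluable population. What remains is that this chain relies on the site thinking to ask, and it specifies no place to record product and date.

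**Neither exposure nor effect is documented.** No participating countries, licensed age range or uptake are given. The licensed vaccine is described only as recombinant and multicomponent, with no statement that it raises hSBA titers against these four strains. A reader might infer that Month 12 persistence is in fact overstated; nothing in the documents shows this. The point rests on what could go unrecorded.

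**The outbreak bullet in 5.10 might be read as permitting an MnB vaccine.** However, the next bullet in 5.10 refers the reader to 5.9 for serogroup B restrictions, and 5.9 is categorical. The outbreak bullet carries no such reference, so the wording needs reconciling, but it is not evidence that such vaccination occurs.

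**The effect is small and the analysis descriptive.** This stands. SAP 2.2.2 plans no formal tests on secondary endpoints, and the shifts calculated above for 1% to 5% vaccinated lie well inside the confidence interval.

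**Conclusion.** The gap is real and consistent across protocol and SAP: a prohibition that runs to Visit 7, secondary endpoints measured at Visit 7, and vaccine recording that ends at Visit 6. A child given another MnB vaccine in between can be counted at Month 12 without a prompted CRF record. In mITT this always happens if the result is valid; in the evaluable set it happens unless the vaccination surfaces through the Visit 7 checks or a deviation report.

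The consequence is limited. The primary endpoints at Visit 6 are unaffected. Any bias in the Month 12 proportions and GMTs would be upward if the other vaccine raises these titers. It would be small against sampling error unless outside vaccination were common, and it would weigh more per child in the smaller Group 2 cells. The size rests on three assumptions that the documents do not supply: the rate of outside vaccination, its effect on the four strains, and true persistence. As the plan stands, the sponsor could not use prompted data to show that the bias is negligible. This is a cheap improvement, not a flaw in the main analysis.

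**What to change.** 1. Extend recording of nonstudy vaccines (name and date) to the Visit 7 blood draw: amend 5.8 and SAP 6.3.2, mark Visit 7 in the Schedule row, and add the instruction to 6.8.
2. Add the follow-up phase to the nonstudy vaccine summaries in SAP 8.2.6.4.
3. In SAP 5.2, define the evaluable population for the Month 12 analysis so that a Visit 7 result obtained after a nonstudy MnB vaccine is excluded, and list those children. mITT would keep them by definition; the listing shows how many there are.
4. Reconcile the outbreak-vaccine bullet in 5.10 with the study-long prohibition in 5.9.

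The cost is one question at a visit that already takes place, on a record already in use to Visit 6, plus the protocol and SAP wording. A few Month 12 results may leave the evaluable set.
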